In case 1600 patients will be included earlier, recruitment may be stopped before December 2016.

CHANGE 2: ADAPT TIME SCHEDULE, SITE NUMBERS AND PATIENT NUMBERS

Section of the protocol: Synopsis

Scheduled study duration	Initiation (FPI): Last patient out (LPO):	September 2014 April 2016
Report	Report available:	July 2016

Was changed to:

Scheduled study duration	Initiation (FPI): Last patient out (LPO):	September 2014 December 2017
Report	Report available:	March 2018

Reasons for change 2:

After 15 months of patient recruitment 1050 / 1600 patients have been included until December 2015. For a meaningful data analysis and interpretation, the targeted patient number of 1600 patients should be met.

Therefore, recruitment time will be prolonged for one more year to 27 months (LPI December 2016), thus study duration will also increase. LPO is now planned for December 2017.

Other timelines will change accordingly.

In case 1600 patients will be included earlier, recruitment may be stopped before December 2016.

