The analysis is performed on the basis of the patient cohorts resulting from the 1:1 matching. Kaplan Meier estimates for the time to discontinuation of treatment (cf. definition in section 5.1.) will be calculated separately for the dabigatran and the VKA patient group and illustrated graphically. In particular, the Kaplan Meier estimates for persistence at time 3, 6, 9 and 12 months will be reported. The comparison in terms of the persistence of patients on treatment with dabigatran versus VKA will be performed by means of the stratified log-rank test, which takes account of the dependency of treatment groups resulting from matching (cf. Klein, Moeschberger, 1997, ²²). Patients who discontinued the study prematurely and for whom no treatment discontinuation is documented will be censored at the time of study discontinuation. Patients who end the study as planned will be censored on the day after the last visit if no previous treatment discontinuation is documented.

The absolute number and proportion of patients discontinuing the initial treatment in the course of the study will be summarised overall and according to the reasons for discontinuation for the dabigatran and VKA cohorts.

The association of patient characteristics (including treatment allocation) with persistence will be investigated by means of Cox regression models (univariate and multivariate models). Baseline characteristics will be presented stratified for patients who discontinue the treatment in the course of the study and those who do not.

A multivariable Cox regression model (including the factors used for calculating the PS and choice of treatment) will be reported as a sensitivity analysis. For this analysis, all patients who are within the common supports of the empirical density function of the PS (instead of matched pairs) will be included; the common support is determined after excluding patients with a propensity score above the 97.5% percentile and below the 2.5% percentile in each treatment group in order to avoid a strong influence from patients with extreme PS values.

Adherence

The analysis is performed on the basis of the patient cohort resulting from 1:1 matching. The Morisky questionnaire consists of 8 questions and will be presented at the time of the 6-month visit. The analysis and categorisation of patients into the categories

- poor adherence (score >2)
- medium adherence (score=1, 2) and
- high adherence (score=0)

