Reasons for change 2:

After 6 months of site and patient recruitment it became evident that the targeted patient and site numbers will not be met and that recruitment time should be longer.

Therefore the planned patient number will be reduced to 1600 and site number to 800.

Recruitment time will be prolonged to 16 months (LPI December 2015), thus study duration will also increase. LPO is now planned for December 2016.

Other timelines will change accordingly.

CHANGE 3: ADAPT TIME SCHEDULE, SITE NUMBERS AND PATIENT NUMBERS

Section of the protocol: Statistics Section Determination of number of patients

It is planned to include a total of 4000 patients in this non-interventional, controlled, observational study (dabigatran etexilate: 2000 patients, VKA: 2000 patients).

Calculation of statistical power:

All analyses are purely exploratory by virtue of the non-interventional study design. On the following assumptions:

- 15% drop-outs /missing values after one year,
- 2000 dabigatran etexilate patients, 2000 VKA patients, with 66% of VKA patients with a matching partner in the dabigatran etexilate group (i.e. total number of patients in the 1:1 matched analysis is 2640)
- a persistence rate of 63% in the dabigatran etexilate group (cf. 1-year persistence with a 60-day permissible medication gap as reported by Zalesak ¹⁹)).

the power for a descriptive p value ≤ 0.05 in a 2-tailed test for the same persistence rates is as follows (dependent on the VKA persistence rate):

Assumed VKA persistence rate*	51%	53.8%	56.5%
Power	100%	99.7%	91.7%

* The calculations were performed with ADDPLAN6 and are based on survival time analysis test statistics and the endpoint variables "Time to permanent treatment discontinuation".

Was changed to:

It is planned to include a total of 1600 patients in this non-interventional, controlled, observational study (dabigatran etexilate: 800 patients, VKA: 800 patients).

Calculation of statistical power:

All analyses are purely exploratory by virtue of the non-interventional study design. On the following assumptions:

- 15% drop-outs /missing values after one year,
- 800 dabigatran etexilate patients, 800 VKA patients, with 66% of VKA patients with a matching partner in the dabigatran etexilate group (i.e. total number of patients in the 1:1 matched analysis is 1056)
- a persistence rate of 63% in the dabigatran etexilate group (cf. 1-year persistence with a 60-day permissible medication gap as reported by Zalesak (¹⁹)).

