the power for a descriptive p value ≤ 0.05 in a 2-tailed test for the same persistence rates is as follows (dependent on the VKA persistence rate):

Assumed VKA persistence rate*	51%	53.8%	56.5%
Power	97.8%	84.8%	61.1%

* The calculations were performed with ADDPLAN6 and are based on survival time analysis test statistics and the endpoint variables "Time to permanent treatment discontinuation".

Reasons for change 3:

After 6 months of site and patient recruitment it became evident that the targeted patient and site numbers will not be met and that recruitment time should be longer.

Therefore the planned patient number will be reduced to 1600 and site number to 800.

Observational Plan

Non-interventional study

Local Amendment

Local Amendment Number:	Local Amendment 2			
Country	Germany			
Date:	04. JAN 2016	 To be implemented only after documented approval of the IRB / IEC / Competent Authorities		
EudraCT No.:	n.a.	 To be implemented immediately in order to eliminate hazard – IRB / IEC / Competent Authority to be notified of change with request for approval		
BI Trial No.:	1160.218			
Investigational Product(s):	Pradaxa®	 Can be implemented without IRB / IEC / Competent Authority approval as changes involve logistical or administrative aspects only		
Title:	Drug persistence/adherence in patients being treated with Pradaxa® (dabigatran etexilate) or vitamin K antagonists (VKA) for stroke prevention in non-valvular atrial fibrillation (AF)			
Rationale for Local Amendment:	
After 15 months of patient recruitment 1050 / 1600 patients have been included until December 2015. For a meaningful data analysis and interpretation, the targeted patient number of 1600 patients should be met.
 
Therefore, recruitment time will be prolonged for one more year to 27 months (LPI December 2016), thus study duration will also increase. LPO is now planned for December 2017.
 
Other timelines will change accordingly.
 
In case 1600 patients will be included earlier, recruitment may be stopped before December 2016.
 
As this amendment is administrative and does not change the content or the nature of this non-interventional study, for readability reasons we refrain from changing every sentence in which site numbers, patient numbers or timelines are mentioned, except for the front page, study synopsis and statistics section.
			
Page 1 of 3				

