7.4 PRIMARY ENDPOINT(S)

The analysis of the primary endpoint will be based on the patient cohort resulting from the 1:1 matching. Time until termination of treatment will be presented for both treatment groups (Dabigatran etexilate vs. VKA) by Kaplan-Meier estimates and displayed graphically, respectively. Especially for time points 3, 6, 9 and 12 months Kaplan-Meier estimates for persistence will be calculated.

The comparison of persistence between the treatments with dabigatran etexilate versus VKA will be conducted by means of the stratified Log-rank test, which takes dependencies resulting from the matching of the treatment groups into account. Patients who discontinue

study prematurely and without documented treatment discontinuation will be censored at study termination. Patients completing the study as planned will be censored at the day after last visit, if no earlier treatment discontinuation is documented. Association between patient characteristics (incl. method of treatment) and persistence will be determined by means of cox regression (univariate and multivariate model). First, univariate regression for each of the independent variables will be performed. Afterwards, all covariates will be entered into a stepwise multivariate regression. The entry level will be $p=0.5$ and the stay level $p=0.1$. Baseline characteristics will be presented stratified by patients who discontinued the study prematurely versus no discontinuation.

A multivariate Cox Regression model (including factors for the calculation of the propensity score and the choice of treatment) will be used as sensitivity analysis. All patients, who are within the “common support” of the empiric PS density function (instead of the matched pairs), will be included in this analysis. The “common support” will be determined after patients with a propensity score above the 97.5% percentile and below the 2.5% percentile have been excluded for each treatment group, respectively. This will be done to avoid high influence of patients with extreme PS.

The following covariates will be used –depending on the sample size- for the Propensity Score Matching and the sensitivity analysis

- CHA₂DS₂-VASC Score (<2, ≥ 2)
- HAS BLED-Score (<3, ≥ 3)
- Age at registration (<65, 65-<75, ≥ 75)
- Previous stroke (Yes, No)
- Treatment (VKA, Pradaxa[®]) (sensitivity analysis only)

and the following covariates will be used –depending on the sample size- for the Cox regression

- CHA₂DS₂-VASC Score (<2, ≥ 2)

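### The 61.1% power at 56.5% VKA persistence does not follow from its stated inputs (about 56%), and the power row does not say which form of log-rank test it assumes

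*Protocol*

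**What the plan says.** Local Amendment 1, Change 3, replaces the sample-size text of protocol section 7.5. Its inputs are:

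- 800 patients per group, 66% of VKA patients matched, so that the "total number of patients in the 1:1 matched analysis is 1056";
- "15% drop-outs /missing values after one year";
- "a persistence rate of 63% in the dabigatran etexilate group";
- a descriptive p-value of at most 0.05, with the power given "in a 2-tailed test for the same persistence rates is as follows (dependent on the VKA persistence rate").

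The resulting row reads 97.8%, 84.8% and 61.1% at VKA persistence of 51%, 53.8% and 56.5%. A footnote names the software (ADDPLAN6) and says that survival-time test statistics were used, but not which log-rank form. The same paragraph states: "All analyses are purely exploratory by virtue of the non-interventional study design".

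The planned comparison in protocol 7.3 is a "stratified log-rank test, which takes account of the dependency of treatment groups resulting from matching", with a textbook reference. SAP 7.4 likewise plans a "stratified Log-rank test, which takes dependencies resulting from the matching of the treatment groups into account". Neither says what the strata are.

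**The concern.** All inputs to the row are printed, so it can be recomputed. Two cells come back almost exactly and the third does not. The third is the smallest difference considered (6.5 points), where a non-significant result is most likely and most easily misread, and the error makes the design look better than it is. Section 7.5 is the only place where the documents quantify what 1600 patients can detect.

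The second question is which test the row describes. The two cells that reproduce match an unstratified log-rank test, while the planned test is stratified. If its strata are the individual pairs, the printed row overstates the power of that test in every cell.

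**Working it through.** **Inputs.** 528 patients per group (1056/2), 12 months of follow-up, 12-month persistence of 0.63 against 0.51, 0.538 or 0.565, 15% drop-out at one year, two-sided 0.05. Assumption not in the documents: exponential times to discontinuation and to drop-out.

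**Direct calculation, unstratified log-rank (Schoenfeld).** With λ = −ln(persistence) and c = −ln(0.85) = 0.1625:

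- P(observed event) = λ/(λ+c) × [1 − exp(−(λ+c))]. For dabigatran λ = 0.4620, giving 0.3436.
- Events D = 528 × (sum of the two probabilities).
- Power = Φ(½ √D |ln HR| − 1.96), with HR = ln(0.63)/ln(VKA persistence).

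| VKA persistence | HR | D | ½√D·abs(ln HR) | Power | Stated |
|---|---|---|---|---|---|
| 51% | 0.686 | 422 | 3.870 | 97.2% | 97.8% |
| 53.8% | 0.745 | 408 | 2.970 | 84.4% | 84.8% |
| 56.5% | 0.809 | 395 | 2.103 | 55.7% | 61.1% |

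Simulation of the third cell gave 54.8% (10,000 runs) and 56.4% (6,000 runs).

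**Can drop-out handling explain 61.1%?** With no drop-out, D = 528 × (0.37 + 0.435) = 425 and power is 58.8%. With events cut by 15%, D = 361 and power is 52.0%. A power of 61.1% needs D = 4 × (2.242/0.2116)² ≈ 449, more events than expected with no drop-out at all. Freedman's formula, two-proportion tests and complementary log-log comparisons, all two-sided, give 50.9% to 58.5%.

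**Check within the current row.** Let z = Φ⁻¹(power) + 1.96. The ratio of z between the 53.8% and 56.5% cells does not depend on sample size and hardly on drop-out.

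- Model: 2.970/2.103 = 1.41.
- Stated powers: 2.988/2.242 = 1.33.
- If 84.8% is right, z for the third cell is 2.988/1.412 = 2.116, so power is Φ(0.156) = 56.2% (56.1–56.3% across model variants). With every rate at the edge of its rounding (63% read as 62.5–63.5%), the most it can reach is 59.4%.

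This check alone does not show which of the two cells is wrong.

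**Check against the row before the amendment (method check only).** At 2640 patients the same formula gives 100%, 99.7% and 91.4%, against 100%, 99.7% and 91.7% printed. Only the patient numbers changed, so z scales by √(1056/2640) = 0.632.

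- 99.7%: 4.708 × 0.632 = 2.977, power 84.6% (current row: 84.8%).
- 91.7%: 3.345 × 0.632 = 2.116, power 56.2% (current row: 61.1%).
- In reverse, 61.1% would have been 94.3% at 2640 patients, not 91.7%.

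Five of the six printed cells fit one method within a point; 61.1% does not.

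**Is 63% a rounded figure?** At 63.4% the third cell becomes 61.1%, but its neighbour becomes 87.5% where 84.8% is stated, and the cell for 2640 patients becomes 94.3% where 91.7% was stated.

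**If each matched pair is a stratum.** A pair contributes only if its first exit is a discontinuation. With no within-pair correlation, P = (λ₁+λ₂)/(λ₁+λ₂+2c) × [1 − exp(−(λ₁+λ₂+2c))] = 0.597, 0.581 and 0.565. That gives 315, 307 and 298 informative pairs out of 528, and power of about 91%, 73% and 44% (simulation 91%, 72–73%, 45%). Positive correlation would raise these values; the documents give no figure for it.

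**The case against.** The failure to reproduce is not in dispute. The case on the other side concerns weight, attribution and the second part.

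- *The first cell is also off.* The stated powers need 445, 413 and 449 events, against 422, 408 and 395 expected, and starting from 97.8% the third cell would be 57.7–58.1%. This is correct. It widens the uncertainty a little, but even that route stays about 3 points below 61.1%.
- *The true software output is unknown.* Also correct. An undisclosed setting could lie behind the cell. The direct calculation, the 84.8% cell and the rescaled 91.7% nevertheless all give about 56%.
- *Other assumptions matter as much.* Taking match rates of 60% to 75% (an assumed range), the third cell runs from 51.8% to 61.1%. But the row is stated for 1056 patients, and a 75% match would put the middle cell at Φ(2.970 × √(1200/1056) − 1.96) = 88.6%, not 84.8%.
- *Pair strata are an assumption.* Correct. The SAP matches on four categorical covariates, so strata of patients with equal scores are conceivable, and planning on a simpler test is common. The 91/73/44% figures are therefore conditional. Not naming the test form is missing detail, not an arithmetic error.
- *Nothing hinges on the row.* Largely right: the analyses are descriptive and the cut to 1600 patients followed recruitment. This keeps the point minor; it does not make the cell correct.

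**Conclusion.** The point holds and is minor. On the stated inputs, power at 56.5% VKA persistence is about 56% (52.0–58.8% across ways of handling drop-out), not 61.1%. This rests on exponential times and an unstratified log-rank test, the combination that reproduces the other five printed cells within a point. At a 6.5-point difference the study is close to a coin toss.

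The row also leaves its test form unnamed, while the planned test is stratified with undefined strata. If each pair is a stratum and within-pair correlation is zero, the row for the planned test is about 91/73/44%. No error rate, decision rule or sample size depends on any of this; what changes is how a non-significant descriptive p-value should be read.

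**What to change.** 1. In section 7.5, restate the third cell as about 56%. If the software run used a setting that is not listed, state that setting instead and recompute the whole row with it.
2. In section 7.5, add a sentence saying that the row is for an unstratified log-rank test on 1056 patients, if that is what was used.
3. In SAP 7.4, add a sentence defining the strata of the planned log-rank test. If each matched pair is a stratum, give about 91/73/44% alongside as a conservative figure, labelled as assuming no within-pair correlation.

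The cost is one corrected cell and two sentences, plus the conditional figures if pairs are the strata. The 1600 patients and the primary test stay as planned; the stated power becomes slightly less favourable.

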2. LIST OF ABBREVIATIONS

Term	Definition / description
AE	Adverse event
AF	Atrial fibrillation
CHA ₂ DS ₂ -VASc-Score	Congestive heart failure, Hypertension, Age (>75), Diabetes mellitus, Stroke/TIA, Vascular disease, Age 65-74, Sex category
CTCAE	Common Terminology Criteria for Adverse events
CTP	Clinical Trial Protocol
FAS	Full Analysis Set
HAS-BLED	Hypertension, Abnormal renal and liver function, Stroke (1 point), bleeding history or predisposition, Labile INR, Elderly (>65 years), Drug and Alcohol
INR	International Normalized Ratio
MedDRA	Medical Dictionary or Regulatory Activities
MG	Matched Group
N	Number
NCI-CTCAE	National Cancer Institute-Common Terminology Criteria for Adverse events
PS	Propensity Score
PT	Preferred Term
SAE	Serious Adverse event
SD	Standard Deviation
SOC	System Organ Class
SUSAR	Suspected Unexpected Serious Adverse Reaction
TS	Treated Set
TSAP	Trial statistical analysis plan
VKA	Vitamin-K-Antagonists
WHO-DD	World Health Organization Drug dictionary

3. INTRODUCTION

As per ICH E9, the purpose of this document is to provide a more technical and detailed elaboration of the principal features of the analysis described in the protocol, and to include detailed procedures for executing the statistical analysis of the primary and secondary variables and other data.

This TSAP assumes familiarity with the Clinical Trial Protocol (CTP), including Protocol Amendments. In particular, the TSAP is based on the planned analysis specification as written in CTP Section 7 "Statistical Analysis". Therefore, TSAP readers may consult the CTP for more background information on the study, e.g., on study objectives, study design and population, treatments, definition of measurements and variables, planning of sample size, randomization.

SAS® Version 9.3 or higher will be used for all analyses.

4. CHANGES IN THE PLANNED ANALYSIS OF THE STUDY

None.

5. ENDPOINT(S)

5.1 PRIMARY ENDPOINT(S)

Proportion of patients, who are still treated with the initial assigned anticoagulant at 12-months visit, derived by Kaplan-Meier estimator for persistence at 12 months, stratified for dabigatran etexilate and VKA. Persistence is defined as the time in months between initiation, i.e. date of first visit, and permanently discontinuation of treatment with Pradaxa® or VKA. Patients who discontinue study prematurely and without documented treatment discontinuation will be censored at date of study termination. Patients completing the study as planned will be censored at the day after last visit, if no earlier treatment discontinuation is documented.

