5.1 Target parameters

5.1.1 Primary and secondary endpoints

Primary endpoint:

- Proportion of patients still being treated at the time of the 12-month visit with the initially allocated anticoagulant, defined as Kaplan Meier estimate at 12 months for persistence, stratified for dabigatran etexilate and VKA. Persistence is defined as the time between initiation and permanent termination of therapy ⁽²⁰⁾. The start of treatment (documented in the CRF of visit 1) is documented as the start date and the date of discontinuation of treatment with Pradaxa® or VKA as the time of permanent termination of therapy

Secondary endpoints:

- Proportion of patients with low, medium or high adherence at the time of the 6-month visit, stratified for dabigatran etexilate and VKA; categorisation is done on the basis of the Morisky questionnaire.
- Reasons for permanent treatment discontinuation.

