6.2 Details of visits

Visit 1 (start of observation)

- Patient data: sociodemographic data (sex, age, height, weight, education, marital status, health insurance status)
- Case history of non-valvular atrial fibrillation (AF): disease onset, data on disease severity (individual components of the CHA₂DS₂-VASc score) and bleeding risk (individual components of the HAS-BLED score)
- Start of treatment with dabigatran etexilate (110 or 150 mg hard capsules) or VKA (start date)
- Concomitant medication: antiarrhythmics, antihypertensives, lipid-lowering agents, other prescription-only medicines
- Number of other prescription-only and frequency of daily administration (other than dabigatran etexilate/VKA)
- Recording of relevant comorbidities (Charlson et al. 1987)²¹

Visit 2 (after about 3 months of use of dabigatran etexilate or VKA)

- Recording of the continuation of therapy with dabigatran etexilate (including dosage) or VKA since visit 1
- Onset of adverse events since visit 1
- Discontinuation of treatment with dabigatran etexilate or VKA since visit 1
 - Reasons for the discontinuation of treatment with dabigatran etexilate or VKA
 - Antithrombotic therapy after discontinuation of treatment with dabigatran etexilate or VKA
 - In the event of treatment discontinuation, all emergent adverse events (AE) are recorded in the eCRF up to 30 days after the end of therapy.

Visit 3 (after about 6 months of use of dabigatran etexilate or VKA)

BI No.: 1160.218

- Recording of the continuation of therapy with dabigatran etexilate (including dosage) or VKA since visit 2
- Onset of adverse events since visit 2
- Discontinuation of treatment with dabigatran etexilate or VKA since visit 2
 - Reasons for the discontinuation of treatment with dabigatran etexilate or VKA
 - Antithrombotic therapy after discontinuation of treatment with dabigatran etexilate or VKA
 - In the event of treatment discontinuation, all emergent adverse events (AE) are recorded in the eCRF up to 30 days after the end of therapy.
- Regular use of dabigatran etexilate or VKA by means of the Morisky score
- Number of prescription-only medicines and frequency of daily administration
- Recording of disease severity (individual components of the CHA₂DS₂-VASc score) and bleeding risk (individual components of the HAS-BLED score)
- Recording of relevant comorbidities (Charlson et al. 1987)²¹

Visit 4 (after about 9 months of use of dabigatran etexilate or VKA)

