6. GENERAL ANALYSIS DEFINITIONS

6.1 TREATMENT(S)

Evaluation/ Method	Visit 1 (Baseline)	Visit 2 (after approx. 3 month)	Visit 3 (after approx. 6 month)	Visit 4 (after approx. 9 month)	Visit 5 (after approx. 12 month)
Socio demography	X				
VHF- anamneses	X				
CHA ₂ DS ₂ VASc- / HAS-BLED- Score	X		X		X
Further comorbidities	X		X		X
Date of start of therapy of Dabigatran etexilate/ VKA (incl. dosing)	X				
Concomitant medication (incl. intake frequency)	X		X		X
Treatment with initial oral anticoagulation		X	X	X	X
Morisky-Score			X		
Date of discontinuation (incl. reason)		X	X	X	X
In case of abortion: therapy after discontinuation		X	X	X	X
Adverse events*		X	X	X	X

* AE data will be collected until 30 days after end of therapy

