6.2 IMPORTANT PROTOCOL VIOLATIONS

Table 6.2: 1 Important protocol violations

Category/ Code		Description	Requirements	Excluded from
A		Entrance criteria not met		
	A1.1	Inclusion criteria not met	Inclusion criteria not met as specified in the protocol.	FAS
	A2	Exclusion criteria not met	Exclusion criteria not met as specified in the protocol	None
B		Informed consent		
	B1	Informed consent not available/not done	Informed consent date missing	All

Patients who received oral anticoagulants for less than 2 months before study inclusion will be treated as minor protocol deviations. These patients will be further documented and the inclusion criterion regarding the prior treatment with anticoagulants will not be set to 'No'. Subjects who were previously treated with oral anticoagulants for two months or more are excluded from the efficacy analysis.

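### SAP 5.1 starts the persistence clock at the first visit instead of the documented treatment start, undeclared; this can overstate persistence for any patient already on the study drug

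*SAP*

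**What the plan says.** - **Protocol 5.1.1.** Persistence runs from initiation to permanent termination of therapy. "The start of treatment (documented in the CRF of visit 1) is documented as the start date". The parenthesis says where the date is recorded; it does not make the visit the start. Protocol 7.3 refers back to this definition for the primary analysis.
- **The start date is its own data item.** Protocol 6.2 lists at visit 1 "Start of treatment with dabigatran etexilate (110 or 150 mg hard capsules) or VKA (start date", and the schedule in SAP 6.1 has a row for "Date of start of therapy of Dabigatran etexilate/ VKA (incl. dosing".
- **SAP 5.1** uses a different origin: "Persistence is defined as the time in months between initiation, i.e. date of first visit, and permanently discontinuation of treatment".
- **SAP 4** reports no changes to the planned analysis, and the SAP history table lists none for section 5.
- **SAP 6.2 on prior use.** "Patients who received oral anticoagulants for less than 2 months before study inclusion will be treated as minor protocol deviations". For them, "the inclusion criterion regarding the prior treatment with anticoagulants will not be set to" No. At the other end, "Subjects who were previously treated with oral anticoagulants for two months or more are excluded from the efficacy analysis". The shorter-term users therefore stay in the Full Analysis Set, from which the matched group is drawn (SAP 6.3).
- **Risk set.** Protocol 7.3 and SAP 5.1 and 7.4 specify right censoring only. Neither document mentions delayed entry.

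**The concern.** The primary endpoint is the Kaplan–Meier estimate of persistence at 12 months, so its time origin is part of its definition. The SAP has replaced the protocol's origin without saying so.

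The replacement matters only where the two dates differ. The clearest case is a patient who was already taking the study drug when enrolled. Under SAP 6.2 that gap can reach just under 2 months. Such a patient is counted as new at visit 1 after surviving the first weeks on treatment, while comparable starters who stopped before enrolment never appear. If stopping is concentrated early, persistence at 3, 6, 9 and 12 months is overstated. The propensity-score covariates in SAP 7.4 (CHA₂DS₂-VASc, HAS-BLED, age, previous stroke) would not be expected to balance the share of such patients between arms.

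A smaller gap can arise in the other direction. Eligibility is considered before the prescription (protocol 6) and the drug comes from a pharmacy (protocol 4.1.4), so some patients may take the first dose shortly after visit 1.

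**Working it through.** **Inputs from the documents.** 12-month persistence is 63% for dabigatran and 56.5%, 53.8% or 51% for VKA, with 1056 matched patients, so 528 per arm (Local Amendment 1, Change 3). Prior use is below 2 months (SAP 6.2). The plan gives no figure for the effect of the clock, so there is none to reproduce.

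**Assumptions, not in the documents.** The stopping hazard is k·h in months 0–2 and h afterwards. A share p of starters enrols late, at time e uniform on 0–2 months, and only if still on drug.

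**Formulas.** S(t) is the probability of still being on drug t months after starting, and E is the mean over e.
- h = −ln S(12) / (2k + 10)
- Visit-1 clock: [(1−p)·S(12) + p·E S(e+12)] / [(1−p) + p·E S(e)]
- Start date without delayed entry: S(12) / [(1−p) + p·E S(e)]

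**Worked case, S(12) = 0.63, k = 2, p = 0.3.** h = 0.46204/14 = 0.0330 per month. E S(e) = 0.93681 and E S(e+12) = 0.60966. The denominator is 0.7 + 0.3 × 0.93681 = 0.98104.
- Visit-1 clock: (0.441 + 0.18290)/0.98104 = 63.60%, which is 0.60 points too high.
- Start date without delayed entry: 0.63/0.98104 = 64.22%, which is 1.22 points too high.

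**All cases (12-month estimate, %).**

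| True | k | Visit-1 clock, p = 0.1 | Visit-1 clock, p = 0.3 | Start date, no delayed entry, p = 0.3 |
|---|---|---|---|---|
| 63 | 1 | 63.00 | 63.00 | 63.72 |
| 63 | 2 | 63.20 | 63.60 | 64.22 |
| 63 | 3 | 63.34 | 64.04 | 64.59 |
| 56.5 | 1 | 56.50 | 56.50 | 57.29 |
| 56.5 | 2 | 56.71 | 57.15 | 57.84 |
| 56.5 | 3 | 56.87 | 57.63 | 58.24 |
| 53.8 | 1 | 53.80 | 53.80 | 54.62 |
| 53.8 | 2 | 54.02 | 54.47 | 55.18 |
| 53.8 | 3 | 54.18 | 54.97 | 55.60 |
| 51 | 1 | 51.00 | 51.00 | 51.84 |
| 51 | 2 | 51.22 | 51.69 | 52.42 |
| 51 | 3 | 51.39 | 52.19 | 52.84 |

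With p = 0.3 and k = 2–3, the 3-month estimate is too high by 0.8–1.7 points. In a simulation of 2,000,000 starters, the start date with entry at visit 1 recovered the true 12-month value within 0.05 points.

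**Treatment difference, p = 0.3, k = 2–3.** If both arms are affected, it shrinks by 0.06–0.16 points (before rounding). If only one arm is, it moves by 0.6–1.2 points. In the 56.5% scenario the true 6.5 points become about 6.4 (both arms), 7.1–7.5 (dabigatran only: 63.60 or 64.04 minus 56.5) or 5.4–5.9 (VKA only: 63 minus 57.63 or 57.15).

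**Scale.** The binomial standard error is √(S(1−S)/528), or 2.10 points at 63% and 2.18 at 51%. It is about 3.0 for the difference, ignoring censoring and pairing.

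**Dependence on the model.** Under a Weibull model with a true value of 63%, suppose 25–50% of the analysed patients had been on drug for 1–2 months. The visit-1 clock gives 63.0% at shape 1, 63.9–65.6% at shape 0.7 and 64.9–68.2% at shape 0.5. The start date without delayed entry gives 63.6–65.5%, 64.3–67.4% and 65.2–69.5%. Direction and ordering are the same. The larger values need a quarter to a half of the cohort to be prior users of the study drug.

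**Start after visit 1.** If every patient started d days late, the SAP clock overstates by S(12 − d/30.44) − S(12). That is 0.2–0.3 points for 3 days and 0.4–0.7 for 7 days (k = 1–3), similar in both arms.

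**The case against.** The strongest reply is that the two dates coincide by design. The protocol describes treatment-naive, newly prescribed patients whose eligibility is considered before the prescription (3.3.2, 4.1.1, 6). The SAP wording can then be read as making initiation operational. For most patients this stands.

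The reply also limits three inferences that a reader might draw.
- **That the analyst has no rule for the origin.** SAP 5.1 gives an explicit one. The defect is an undeclared departure from the protocol, not an undefined analysis.
- **That the SAP has two competing origins, because 7.8 counts adverse events from the start of treatment.** That passage defines a treatment-emergent window, which is a different quantity.
- **That SAP 6.2 admits patients already on the study drug.** It speaks of oral anticoagulants in general. A patient who took another anticoagulant for some weeks and is newly prescribed the study drug at visit 1 has no left truncation. No passage shows that anyone was already on the study drug.

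The SAP clock is also less biased than the protocol's start date used without delayed entry, so restoring the protocol wording alone would not be an improvement for these patients. And 30% is a high share for a group classed as protocol deviations.

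The reply does not remove the discrepancy in the definition of the primary endpoint, or the fact that SAP 6.2 foresees prior users and keeps them.

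**Conclusion.** The time origins differ, the change is not declared, and neither document provides for delayed entry. These points rest on the text alone.

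The size is unknown and probably small. It depends on how many patients were already on the study drug, possibly none, and on the shape of the stopping hazard; the documents give neither. Under a constant hazard the visit-1 clock has no bias. With a 2–3 times higher early hazard the 12-month estimate is too high by about 0.2–0.4 points with 10% late and 0.6–1.2 with 30% late, below one per-arm standard error. The treatment comparison is hardly affected unless the late share differs by arm, so a conclusion that the comparison is biased is not supported. All analyses are descriptive (protocol 7), so the matter concerns the accuracy of the reported estimates. Severity: minor.

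**What to change.** - In SAP 5.1 and 7.4, set time zero to the documented start date of the initial anticoagulant. Patients who started it before visit 1 enter the risk set at visit 1 in the Kaplan–Meier, log-rank and Cox analyses. Do not restore the start date without this delayed entry.
- For patients who start after visit 1, use the start date only where an actual date is recorded. The date is collected only at visit 1, so the entry may be an intended date.
- Report by arm the number of patients whose start date precedes visit 1 and the number with prior oral anticoagulation. Add a sensitivity analysis without prior users.
- Declare the time origin and the prior-use rule in SAP 4.

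The cost is SAP wording and one entry-time variable built from a date already collected. SAP 6.2 implies that prior anticoagulation and its duration are known. A breakdown by drug may not be possible: protocol 6.1 says that prior medication is recorded, but the visit-1 list in 6.2 names only "Concomitant medication: antiarrhythmics, antihypertensives, lipid-lowering agents, other prescription-only medicines". Slightly fewer patients are at risk in the first weeks, and a matched pair informs the stratified log-rank test only once both members have entered.
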